Appendix 1: Inclusion/Exclusion Criteria Referral Form

Inclusion/Exclusion Criteria Referral Form: IMPROVment® Class Participation

PATIENT NAME: _____ DATE: _____
 PATIENT DOB: _____
 PARENTS NAMES: _____
 ADDRESS: _____
 PHONE: _____

Inclusion Criteria

_____ Yes	_____ No	- Age: 50+
_____ Yes	_____ No	- Parkinson's Disease Diagnosis
_____ Yes	_____ No	- Hoehn Yahr Score between 1 and 3
_____ Yes	_____ No	- Cognitive status: able to follow simple commands like
_____ Yes	_____ No	- Walks at least 3 meters independently

Exclusion Criteria

_____ Yes	_____ No	- History of adverse effects related to physical activity
_____ Yes	_____ No	- Severe comorbidities

Appendix 2: Class Structure

Warm up: (25 minutes)

- Finding group breath
- Alternating squeezes, raining, and patting up and down entire body with hands
- Head dance moving up and down/side to side
- Make different faces
- Swimming with arms (forward & backward circles)
- Circular and angular movements with UE (alternating between these)
 - Elbows
 - Wrists
 - Fingers
 - Combination
- Catching lightening bugs
 - Reaches outward → starting to challenge seated balance
- Mime box around you
 - Reaching high, low, twisting through spine
- Activity
 - Make a meal, do your morning routine, favorite leisure activity
- Heel toe the feet out and in to each other
- Leg dance- bending and lengthening through the knees
 - Adding knee lifts into chest
- Circular and angular movements with UE (alternating between these)
 - Knees
 - Ankles
 - Combination
- Moving one arm and one leg
 - Variations of combinations of this
- Stretches
 - Legs
 - Figure 4 stretch
 - Leg out in front and flex ankle (option to stretch forward)
 - Seated lunge

Standing Barre Work (10 mins)

- Releves and plies
- Painting with toe on floor
- Lifting toe off the floor
- Chair duet

Center Work (20 mins)

- Group sculpture
- Mirroring
- Find a shape and match someone else's
- Mold person into shape and then match the shape
- Group flocking
- Pass the energy

Cool Down (5 mins)

- Repeat stretches
- Group breaths

Appendix 3: Adverse Event Reporting Form

Adverse Event Reporting Form

ID for PD

Date of the event: _____ Date resolved: _____ Date staff informed: _____

Is this a serious adverse event? Yes No

If yes, circle type of event:

- a. Death
- b. Hospitalization
- c. Life threatening illness or accident
- d. A permanent disability or incapacity
- e. Abnormal laboratory or diagnostic test result requiring immediate medical attention
- f. Other serious illness that might have resulted in an SAE without aggressive medical

Intervention

Did the participant receive treatment for AE/SAE? Yes No

If yes, where: _____

If hospitalized: Date of admission: _____ Date of discharge: _____

List below all therapy/medications taken by the patient related to this adverse event. (Attach additional pages if necessary)

Medication	Dose/ Route/ Frequency	Start Date	Stop Date	Indication

Any medical history related to the event? Yes No

If yes, explain _____

ACTION TAKEN (circle all that apply):

- a. None
- b. Medical Intervention
- c. Hospitalization
- d. Intervention discontinued
- e. Other _____

OUTCOME (circle appropriate response):

- a. Recovered without treatment
- b. Recovered with treatment
- c. Still present, no treatment
- d. Still present, being treated
- e. Residual effect(s) present, no treatment
- f. Residual effect(s), present, being treated
- g. Subject died

Need to follow-up? Yes NO _____

Grade the severity of the adverse event:	Grade the association of the adverse event with the intervention:
Mild	
Moderate	
Severe	
Life-threatening or disabling	
Fatal	

Principal Investigator's Signature: _____ Date: _____

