Classes will take place at the APDA in their group fitness room. Participants will use chairs and music during the class. Class will be instructed by an occupational therapy (OT) student that has trained as a dancer for 20 years and is certified to administer the IMPROVment® method after attending an in-person training by its original creators and continues to receive feedback to better the administration of IMPROVment®⁷. Class will begin and end with participants sitting in a circle formation to eliminate any feelings of hierarchy among the participants by creating a unified group. The classes consist of three parts: seated exercise, standing barre work, and across the floor movement (refer to Table 1). Movement cues are given by the instructor to the participants and progress through the themes of isolation, shape, time, flow, space/direction, and effort (refer to Table 2). Classes will be structured by using a set class protocol created by the IMPROVment team to ensure consistency in the method delivery. Music that is popular with the age demographic will be played throughout the entire class. Trained OT students in the Cognitive and Occupational Performance Lab (PI: [name]) and the APDA's certified physical therapist ([name], DPT) will attend all classes to ensure participant safety.

Please see Appendix 2 for a detailed list of exercises that comprise class structure.

F4 Safety and Adverse Events

4.a Safety and Compliance Monitoring

Trained occupational therapy graduate students in the Cognitive and Occupational Performance Laboratory (PI: [name]) and the APDA's certified physical therapist ([name], DPT) will attend all classes to ensure participant safety. We do not anticipate any serious adverse events; however, class participation may increase the risk for falls and minor resulting injuries (e.g., bruises, scrapes). We expect this occurrence to be low if at all present, as the participants have relatively low fall risk and precautionary measures are in place to prevent falls (i.e. certified PT and OT students present at all times to monitoring participants' safety, safety modifications [e.g. sitting in a chair]).

4.b Medical Monitoring

NA

4.c Definitions of Adverse Events

NA

4.d Classification of Events

NA

4.e Data Collection Procedures for Adverse Events

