See Adverse Event Reporting Form in Appendix 3. Data on the number and type of adverse events will be collected and reported when study results are disseminated.

4.f Reporting Procedures

See Adverse Event Reporting Form in Appendix 3.

4.g Adverse Event Reporting Period

Adverse events will be reported to the PI immediately (within one day), and the participant will be encouraged to report them to his/her primary care physician or neurologist within the week.

4.h Post-study Adverse Event

NA

G Statistical Plan

G1 Sample Size Determination and Power

Each group will have 7-10 participants, a typical size for ID classes. This ensures enough participants to create a cohesive group, but also to provide an appropriate level of safety. Since this is a pilot study, power analyses were not conducted. Rather, data from this study can be used to power future studies. Although attrition is not anticipated, we aim to recruit 10 participants per group to ensure there are at least 7 participants in the class.

G2 Interim Monitoring and Early Stopping

NA

G3 Analysis Plan

Aim 1: Investigate the effects of IMPROVment® on cognition for people with PD.
Cognition will be assessed at pre (T1) and post (T2) using the NIH (CB), AUT, and WCPA. Scores obtained in these assessments will be compared across time point and group using mixed model ANOVA.

Aim 2: Investigate the effects of IMPROVment® on daily functions for people with PD.
Daily function will be measured at pre (T1) and posttest (T2) using the OARS-EX and SPDSA. Scores will be compared across time point and group using mixed model ANOVA.

G4 Statistical Methods

See above. Analysis will be conducted with IBM SPSS software.

G5 Missing Outcome Data

Participants with missing data will be excluded from analyses involving those data. Since this is a small pilot study, we intend to maximise the use of data we can collect.

G6 Unblinding Procedures

NA (this is not a blinded study)

H Data Handling and Record Keeping

H1 Confidentiality and Security

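### The adverse event form asks for an event type only when the event is serious, so non-serious falls and minor injuries are not captured by type in any standard way, although section 4.e promises number and type

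*Combined protocol and SAP*

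**What the plan says.** All references are to the combined protocol and SAP.

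- **What is promised.** Section F4, 4.e: "Data on the number and type of adverse events will be collected and reported when study results are disseminated". The sentence is not limited to serious events.
- **Where it is recorded.** Sections 4.e and 4.f both give the same pointer: "See Adverse Event Reporting Form in Appendix 3". No other instrument is named. Section H3 (case report forms and source documents) is NA.
- **What is foreseen.** Section 4.a: "We do not anticipate any serious adverse events". It then says that "class participation may increase the risk for falls and minor resulting injuries (e.g., bruises, scrapes", and adds: "We expect this occurrence to be low if at all present". The risk section (E2, 2.e) also names falls as a risk, while saying that they are not expected during the classes.
- **What the form asks.** Appendix 3 opens with dates and a yes/no question on seriousness, followed by "If yes, circle type of event" and six options.
- **What might have supplied a type.** Sections 4.c (definitions) and 4.d (classification) are both NA.

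**The concern.** The promise covers every adverse event, but the item that records type is open only to serious ones. The plan anticipates no serious events. The type item therefore serves events that the plan thinks unlikely to arise and is skipped for the falls and minor injuries that it names.

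At stake is a small but useful safety result. Section G1 justifies the sample size by saying that this is a pilot whose data can be used to power future studies. How many falls occurred, and how many of them in class, is something the next study would want to know.

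**Working it through.** No figure in the plan needs reproducing. The check sets the fields of the form against the promise in 4.e.

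**Step 1: the fields of Appendix 3, as extracted.**

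| Field | Applies to | Says what happened? |
|---|---|---|
| Dates (event, resolved, staff informed) | all events | no |
| Serious, yes or no | all events | no |
| Type, six options | serious events only | mostly no (step 3) |
| Treatment received, and where | all events | no |
| Medications, with indication | all events with medication | only indirectly |
| Related medical history | all events | no, asks for history |
| Action taken | all events | no |
| Outcome | all events | no |
| Need for follow-up | all events | no |
| Severity grade | all events | no |
| Association with the intervention | all events | no |

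Items that ask for type: serious events, 1 (with six options); non-serious events, 0. Items that ask for a description of the event: 0 for either kind.

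**Step 2: two hypothetical non-serious events.** Event A is a fall in class with a bruise. Event B is a sore shoulder after the seated exercises. Suppose that both are untreated, mild, resolved, and given the same association grade. Each form then reads: not serious; type skipped; no treatment; no medication; no related history; no action; recovered without treatment; mild. Apart from the dates, the two completed forms are identical. The fall cannot be told from the sore shoulder unless someone adds a note that the form does not request.

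**Step 3: serious events.** The six options are death, hospitalization, a life-threatening illness or accident, lasting disability, an abnormal test result, and another serious illness. Most of these say why an event counts as serious, not what it was. A fall that led to admission would be circled as hospitalization, and nothing would identify it as a fall. So the gap is not confined to non-serious events.

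**Step 4: other sources in the plan.** Sections 4.a to 4.h give no list of categories. The reporting rule in 4.g sets a time limit but says nothing about content.

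**Step 5: the summary that would be lost.** With 7 to 10 participants per group (G1) and 12 classes each, the scheduled exposure is 2 × 7 × 12 = 168 to 2 × 10 × 12 = 240 person-classes, counting both groups. The denominator for a rate of falls in class is available. The numerator is not reliably available from the form.

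**The case against.** **The form was damaged in extraction.** The association options are missing, one option in the serious list breaks in mid-phrase, and no participant identifier is visible. A description line may also have been lost. This stands as a caution: the original must be checked first. The rest of the form reads continuously, however, and shows no sign of a dropped line.

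**Staff would know what happened.** A physical therapist and trained students attend every class, the principal investigator hears within a day and signs the form, and there are write-in spaces. A reader might infer from the form that type is lost for every non-serious event and cannot be reported at all. The documents do not support that, since type could survive in notes or memory. What remains is that nothing asks for it, so its capture depends on who completes the form.

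**Type may mean serious or not, or the severity grade.** The form does record both. But its own type item is separate from each of them, so this reading does not fit the form's use of the word.

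**The plan does not expect falls.** This is right. Section 4.a treats them as possible and infrequent, and 2.e says that they are not expected. A reader who took falls to be anticipated events would go beyond the text.

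**Modified participation.** The action list includes "d. Intervention discontinued" and no option for a modified class, so a reader might infer that a change to seated participation cannot be recorded. The next option is Other, with a write-in space, and it covers this. Nor do the documents rank seated modification as the main precaution; it is one of several listed.

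**More detail is a matter of taste.** This also stands for the part of the class in which an event occurred and for finer injury subtypes. Section 4.e promises number and type only.

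**Conclusion.** The mismatch is real and minor. Completed exactly as written, the form gives a count of non-serious events with severity, outcome and association, but not what they were. The type report promised in 4.e, and in particular a count of falls, could not reliably be produced from it.

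It is minor because few events are likely, the group is small and observed in class, and the analyses in G3 concern cognition and daily function only. The conclusion assumes that the extracted form is complete apart from the visible damage, and that type in 4.e means the nature of the event. If the original carries a description line for all events, the main gap closes. The NA entries in 4.c and 4.d would then still leave the categories undefined.

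**What to change.** 1. Check the original Appendix 3 for any description or identifier field lost in extraction.
2. If there is no description field, add for every event, serious or not: a one-line description, a short category list (fall, other injury, other), and whether the event occurred in class.
3. Replace the NA in 4.c and 4.d with a reference to these categories, so that the form and the 4.e report use the same terms.

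This changes what is recorded, not how participants are managed. The cost is a minor form revision and an IRB amendment, plus about a minute per event. No extra staff are needed.

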Appendix 4: VAS Mood Scales

VAS Scales for PD Symptoms and Comfort

Record ID

Date

Before

After

1

1. happy/sad

Please rate the way you feel at this moment
from 'very sad' to 'very happy'

very sad

very happy

(Place a mark on the scale above)

2. calm/nervous

Please rate the way you feel at this moment from 'very calm' to 'very nervous'

very calm

very nervous

(Place a mark on the scale above)

3. lively/sluggish

Please rate the way you feel at this moment from 'very lively' to 'very sluggish'

very lively

very sluggish

(Place a mark on the scale above)

4. overall well being

Please rate the way you feel at this moment from feeling 'very poorly' to 'very well'

very poorly

very well

(Place a mark on the scale above)

L4 Questionnaires and Written Assessments

Quesitonnaire 1: Older Americans Resources and Services Scale- Extended Version (OARS-Ex)

Now I'd like to ask you about some of the activities of daily living, things that we all need to do as part of our daily lives. I would like to know if you can do these activities without any help at all, or if you need some help to do them, or if you can't do them at all.

1. Can use the telephone...
 - 1 no difficulty (including looking up numbers and dialing)
 - 2 slower or with greater difficulty
 - 3 need some help (can answer the phone or dial operator in an emergency, but need a special phone or help in getting the number or dialing)
 - 4 need moderate help
 - 5 or are you completely unable to use the phone
2. Can get to places out of walking distance...
 - 1 without help (can travel on buses, taxis, or drive your own car)
 - 2 slower or with greater difficulty
 - 3 with some help (need someone to help you or go with you when traveling)
 - 4 need moderate help
 - 5 or are you unable to travel unless emergency arrangements are made for a specialized vehicle like an ambulance?
3. Can go shopping for groceries or clothes (assuming has transportation)...
 - 1 without help (taking care of all shopping needs yourself, assuming you had transportation)
 - 2 slower or with greater difficulty
 - 3 with some help (need someone to go with you on all shopping trips)
 - 4 need moderate help
 - 5 or are you completely unable to do any shopping?
4. Can prepare your own meals...
 - 1 without help (plan and cook full meals yourself)
 - 2 slower or with greater difficulty
 - 3 with some help (can prepare some things but unable to cook full meals yourself)
 - 4 need moderate help
 - 5 or are you completely unable to prepare any meals?
5. Can do your own housework...
 - 1 without help (can scrub floors, etc.)
 - 2 slower or with greater difficulty
 - 3 with some help (can do light housework but needs help with heavy work)
 - 4 need moderate help
 - 5 or are you completely unable to do any housework?
6. Can take your own medicine...
 - 1 without help (in the right doses at the right time)
 - 2 slower or with greater difficulty
 - 3 with some help (able to take medicine if someone prepares it for you and/or reminds you to take it)
 - 4 need moderate help
 - 5 or are you completely unable to take your own medications?

7. Can handle your own money...

- 1 without help (write checks, pay bills, etc.)
- 2 slower or with greater difficulty
- 3 with some help (manage day to day buying but need help with managing checkbook and paying bills)
- 4 need moderate help
- 5 or are you completely unable to handle your own money?

8. Can you eat ...

- 1 without help (able to feed yourself completely)
- 2 slower or with greater difficulty
- 3 with some help (need help with cutting, etc.)
- 4 need moderate help
- 5 or are you completely unable to feed yourself?

9. Can you dress and undress yourself ...?

- 1 without help (able to pick out clothes, dress and undress yourself)
- 2 slower or with greater difficulty
- 3 with some help
- 4 need moderate help
- 5 or are you completely unable to dress and undress yourself?

10. Can you take care of your own appearance, for example combing your hair and (for men) shaving ...

- 1 without help
- 2 slower or with greater difficulty
- 3 with some help
- 4 need moderate help
- 5 or are you completely unable to maintain your appearance yourself?

11. Can you walk ...

- 1 without help (except from a cane)
- 2 slower or with greater difficulty
- 3 with some help from a person or with the use of a walker, or crutches, etc.
- 4 need moderate help
- 5 or are you completely unable to walk?

12. Can you get in and out of bed ...?

- 1 without any help or aids
- 2 slower or with greater difficulty
- 3 with some help (either from a person or with the aid of some device)
- 4 need moderate help
- 5 or are you totally dependent on someone else to lift you?

13. Can you take a bath or shower ...?

- 1 without help
- 2 slower or with greater difficulty
- 3 with some help (need help getting in and out of the tub, or need special attachments on the tub)
- 4 need moderate help
- 5 or are you completely unable to bathe yourself?

14. Do you ever have trouble getting to the bathroom on time?

N/A I have a catheter or colostomy

- 1 never
- 2 occasionally
- 3 sometimes
- 4 often
- 5 always

Written Assessment 1: Unified Parkinson's Disease Rating Scale (UPDRS) - III. MOTOR EXAMINATION

Unified Parkinson's Disease Rating Scale (UPDRS) - III. MOTOR EXAMINATION

	18. Speech 0 = Normal 1 = Slight loss of expression, diction and/or volume. 2 = Monotone, slurred but understandable; moderately impaired 3 = Marked impairment, difficult to understand 4 = Unintelligible
	19. Facial expression 0 = Normal 1 = Minimal hypomania, could be normal "Poker Face" 2 = Slight but definitely abnormal diminution of facial expression 3 = Moderate hypomania; lips parted some of the time 4 = Masked or fixed faces with severe or complete loss of facial expression; lips parted $\frac{1}{4}$ inch or more
 Face  RUE  LUE  RLE  LLE	20. Tremor at rest 0 = Absent 1 = slight and infrequently present 2 = Mild in amplitude and persistent. Or moderate in amplitude, but only intermittently present 3 = Moderate in amplitude and present most of the time 4 = Marked amplitude and present most of the time
 Right  Left	21. Action or postural tremor 0 = Absent 1 = Slight; present with action 2 = Moderate in amplitude, present with action 3 = Moderate in amplitude with posture holding as well as action 4 = Marked in amplitude, interferes with feeding
 Neck  RUE  LUE  RLE  LLE	22. Rigidity (Judged on passive movement of major joints with subject relaxed in sitting position. Cog wheeling to be ignored). 0 = Absent 1 = Slight or detectable only when activated by mirror or other movements 2 = Mild to moderate 3 = Marked, but full range of motion easily achieved 4 = Severe, range of motion achieved with difficulty

Unified Parkinson's Disease Rating Scale (UPDRS) - III. MOTOR EXAMINATION

 Right  Left	
23. Finger taps (Subject taps thumb with index finger in rapid succession with widest amplitude possible, each hand separately.)
 
0 = Normal 1 = Mild slowing and/or reduction in amplitude 2 = Moderately impaired. Definite and early fatiguing - may have occasional arrest in movement. 3 = Severely impaired. Frequent hesitation in initiating movements or arrest in ongoing movement 4 = Can barely perform the task

 Right  Left	
24. Hand Movements (Subject opens and closes hand in rapid succession with widest amplitude possible, each hand separately.)
 
0 = Normal 1 = Mild slowing and/or reduction in amplitude 2 = Moderately impaired. Definite and early fatiguing - may have occasional arrests in movement 3 = Severely impaired. Frequent hesitation in initiating movements or arrests on on-going movements. 4 = Can barely perform the task

 Right  Left	
25. Rapid alternating movements of hands (Pronation - supination movements of hands, vertically or horizontally, with as large an amplitude as possible, both hands simultaneously.)
 
0 = Normal 1 = Mild slowing and/or reduction in amplitude 2 = Moderately impaired. Definite and early fatiguing - may have occasional arrests in movement 3 = Severely impaired. Frequent hesitation in initiating movements or arrests on ongoing movements 4 = Can barely perform the task

 Right  Left	
26. Leg ability (Subject taps heel or ground in a rapid succession, picking up entire leg. Amplitude should be about 3 inches.)
 
0 = Normal 1 = Mild slowing and/or reduction in amplitude 2 = Moderately impaired. Definite and early fatiguing - may have occasional arrests in movement 3 = Severely impaired. Frequent hesitation in initiating movements or arrests on on-going movements 4 = Can barely perform the task

Unified Parkinson's Disease Rating Scale (UPDRS) - III. MOTOR EXAMINATION

	27. Arising from chair (Subject attempts to arise from straight-back wood or metal chair with arms folded across chest.) 0 = Normal. 1 = Slow, or may need more than one attempt. 2 = Pushes self up from arms of seat. 3 = Tends to fall back and may have to try more than one time, but can get up without help. 4 = Unable to arise without help.
	28. Posture 0 = Normal. 1 = Not quite erect, slightly stooped posture; could be normal for older person. 2 = Moderately stooped posture, definitely abnormal; can be slightly leaning to one side. 3 = Severely stooped posture with kyphosis; can be moderately leaning to one side. 4 = Marked flexion with extreme abnormality of posture.
	29. Postural stability (Response to sudden posterior displacement produced by pull on shoulders while subject erect with eyes open and feet slightly apart. Subject is prepared.) 0 = Normal 1 = Retropulsion, but recovers unaided. 2 = Absence of postural response, would fall if not caught by examiner. 3 = Very unstable, tends to lose balance spontaneously. 4 = Unable to stand without assistance.
	30. Gait 0 = Normal 1 = Walks slowly, may shuffle with short steps, but no festination or propulsion. 2 = Walks with difficulty, but requires little or no assistance; may have some festination, short steps, or propulsion. 3 = Severe disturbance of gait, requiring assistance. 4 = Cannot walk at all, even with assistance.

Unified Parkinson's Disease Rating Scale (UPDRS) - III. MOTOR EXAMINATION

	31. Body, bradykinesia and hypokinesia (Combining slowness, hesitancy, decreased arm swing, small amplitude and poverty of movement in general.) 0 = Normal 1 = Minimal slowness, giving movement a deliberate character; could be normal for some persons. Possibly reduced amplitude. 2 = Mild degree of slowness and poverty of movement which is definitely abnormal. Alternatively, some reduced amplitude. 3 = Moderate slowness, poverty or small amplitude of movement. 4 = Marked slowness, poverty or small amplitude of movement.

Written Assessment 2: Alternate Uses Task

Alternate Uses Task

"In this task, you will be given the names of four common objects, one at a time. You will have 3 minutes to think of as many uses as possible for each object, especially thinking about creative uses. There are many common and obvious uses for each object that you can list. You are encouraged to also think of as many creative ideas for using these objects as you can. Creative ideas are ideas that strike people as clever, unusual, interesting, uncommon, humorous, innovative, or different. While being creative, the uses also need to be realistic. For example, if the object was a tire, you would not say it could be a ring, because that is not actually possible. While it could be a ring for a giant, this is also not possible as giants are imaginary. The uses also need to be specific – avoid general or vague answers. So for the tie, you should not say "to play with," but you could instead say "to use as a swing." Try to let your thoughts flow freely to say as many creative uses for each object as you can. Don't worry if you think your answer sounds silly or think it might be wrong. Just try to keep naming as many uses as you can think of. Do you have any questions?"

**Place the page with the object name in front of the participant. Allow 3 minutes to verbally state as many uses as possible. Record responses on the response sheet. If no new response is made for 15 seconds, gently prompt the participant, saying "how else could you use this object?" if another 15 seconds pass with no new response, prompt "remember, don't worry if it sounds silly." After the third 15 second pause, ask the participant if they would like to discontinue to task. Record the total amount of time allowed for the trial and proceed to the next object. Be sure to record the total time allowed for each object.*

Newspaper

1.	10.
2.	11.
3.	12.
4.	13.
5.	14.
6.	15.
7.	16.
8.	17.
9.	18.

Total time for Newspaper: _____

Brick

1.	10.
2.	11.
3.	12.
4.	13.
5.	14.
6.	15.
7.	16.
8.	17.
9.	18.

Total time for Brick: _____

Rope

1.	10.
2.	11.
3.	12.
4.	13.
5.	14.
6.	15.
7.	16.
8.	17.
9.	18.

Total time for Rope: _____

Bed Sheet

1.	10.
2.	11.
3.	12.
4.	13.
5.	14.
6.	15.
7.	16.
8.	17.
9.	18.

Total time for Bed Sheet: _____

M References

1. Tanner, C. M. & Aston, D. A. (2000). Epidemiology of Parkinson's disease and akinetic syndromes. *Current Opinion in Neurology*, 13, 427-430. doi: 10.1016/S0733-8619(05)70259-0
